Exclusion criteria	Exclusion criteria	HIRA database	
Claims with the following KCD codes or procedure codes:
 
 
1. Valvular AF/ Prosthetic heart valves: I05, I08, I09, I34, Q23, T820, T826, Z952, Z953, Z954            - Korean procedure codes: M6580, M6581, M6582, O1791, O1792, O1793, O1794, O1795, O1796, O1797, O1798, O1799, M6531, M6532, M6533, O1690, O1730, 1740, O1750, O1760, O1770, O1781, O1782, O1783, O1810, O1826
 
2. End-stage of chronic kidney disease/dialysis: N185, T824, Y602, Y612, Y622, Y841, Z49, Z992, E1022, E1122, E1222, E1322, E1422
 
3. Kidney transplant: Z940
 
4. Venous thromboembolism: I636, I676, I801, I802, I803, I808, I809, I81, I822, I823, I829, I26
 
5. Hip or knee replacement            - Korean procedure codes: N0711, N0715, N1711, N1715, N1721, N1725, N2070, N2072, N2077, N2710, N2712, N2717, N3710, N3712, N3717, N3720, N3722, N3727, N4710, N4712, N4717, N4720, N4722, N4727
 
6. Thyrotoxicosis: E05
 
7. Pericarditis: I30, I31, I32
 
8. Hypertrophic cardiomyopathy: I422
 
9. Elective defibrillation, radiofrequency ablation, or left atrial appendage occlusion            - Korean procedure codes: M5880, M6540, M6542, M6545, M6547, M6511
 

Follow-up period	Follow-up period	HIRA database	
From the index date until the first occurrence of the following whichever came first:
 
 
1. Discontinuation: maximum of a 30-day gap after the calculated time to finishing the pack based on pack size and number of tablets per day. Switching: switch to any other study drugs
 
2. Outcome occurrence
 
3. Study ends: November 30, 2016
 

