2.1 STUDY DESIGN

This study will use a retrospective cohort design in which the treatment effectiveness and safety outcomes of new use of NOACs compared to other NOACs, new use of warfarin, and aspirin will be estimated in patients with atrial fibrillation using the Korean Health Insurance Review & Assessment Service (HIRA) database. Comparative analyses will be performed contingent on a feasibility assessment based on the descriptive analyses. Propensity score method and Cox proportional hazards models will be used to account for selection bias, differences in follow-up time, and right data censoring. This will allow us to minimize selection bias and confounding bias and provide outcome data amenable to rapid clinical interpretation (i.e., time-to-event analysis, hazard ratios). Furthermore, HIRA database will allow us to preserve the population-based longitudinal data collection advantages. The overall study design is described in Figure 1.

[figure not shown]

Figure 1. Study design scheme

Study population

Subjects with atrial fibrillation (between January 1, 2007 up to and including the index date*) who newly initiated NOACs, warfarin, or used aspirin between July 1, 2015 and November 30, 2016 in the Korean Health Insurance Review & Assessment Service (HIRA) database.

*Index date is the first prescription date of study drugs, including NOACs, warfarin, and aspirin.

Data source

South Korea has a universal health coverage system that the National Health Insurance covers approximately 97% of the overall South Korean population. The claims data of Health Insurance Review & Assessment Service (HIRA) contains 46 million patients per year that account for 90% of the total population in Korea and include claims from almost 80,000 healthcare service providers across South Korea as of 2011.

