 - A. Sub-dataset 7: patients with index treatment of apixaban and patients with index treatment of aspirin
 - B. Sub-dataset 8: patients with index treatment of dabigatran and patients with index treatment of aspirin
 - C. Sub-dataset 9: patients with index treatment of rivaroxaban and patients with index treatment of aspirin

[NOTE] The index date will be defined as date of the first prescription of NOAC or aspirin in patients with NVAF during the intake period (from July 1, 2015 to November 30, 2016). To identify NOAC users, a look-back observation period from 1 year prior to the day before the index date will be used and must indicate no OAC use during this period. However, OAC use or antiplatelet use during a look-back observation period from 1 year prior to the day before the index date will be allowed for aspirin users. The diagnosis date of NVAF could occur from January 1, 2007 up to and including the index date.

Each patient was followed until discontinuation or switching of index treatment, outcome occurrence, or study ends (November 30, 2016).

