4.3 OTHER ENDPOINTS

Table 3. Other Endpoints

Variable	Role	Operational definition
Discontinuation	Outcome	Discontinuation is defined as the first day of a period of at least 30 consecutive days after the calculated time to finishing the pack based on pack size and number of tablets per day. The date of discontinuation will be the end date of the last filled prescription before the treatment gap.
Switching	Outcome	A switch among anticoagulants will be defined as a prescription filled for non-index OAC within 30

Variable	Role	Operational definition
		days after the date of discontinuation.
Clinical events preceding each pattern	Outcome	
Types of event* preceding each pattern (i.e., discontinuation, switching)
 
[*Note] Events will include but not limited to (1) serious clinical events where physicians might consider changing anticoagulants (e.g., thromboembolic events (e.g., stroke/systemic embolism, venous thromboembolism [codes in Table 7]), major bleeding [codes in Table 8]); (2) the occurrence of a contraindication for OACs (e.g., valvular atrial fibrillation, severe kidney disease); and (3) procedure for atrial fibrillation that might not require OACs (e.g., elective defibrillation, radiofrequency ablation, and left atrial appendage occlusion [codes in Table 13]).

Compliance (medication possession ratio, MPR)	Outcome	
Medication possession ratio (MPR) will be calculated as total days of index treatment dispensed / 365 days of study follow-up.
 
Patients with an MPR greater than 1 will be capped at 1.

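### SAP Table 3 recognises a switch only after the index supply has run out, so OAC switches filled earlier are missed or dated late, and the rule conflicts with the protocol's follow-up definition

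*SAP*

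**What the plan says.** **SAP 4.3, Table 3 (Switching, role: outcome).** "A switch among anticoagulants will be defined as a prescription filled for non-index OAC within 30" "days after the date of discontinuation". Only OACs count, and the window opens at discontinuation.

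**SAP 4.3, Table 3 (Discontinuation).** "Discontinuation is defined as the first day of a period of at least 30 consecutive days after the calculated time to finishing the pack". The dating rule is: "The date of discontinuation will be the end date of the last filled prescription before the treatment gap".

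**SAP 3.1, Cohorts.** "Each patient was followed until discontinuation or switching of index treatment, outcome occurrence, or study ends (November 30, 2016"). Switching is a separate reason for ending follow-up, but it is not defined there and there is no reference to Table 3. Table 3 holds the only definition of switching in the SAP.

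**Protocol 8.3, Follow-up period.** "Switching: switch to any other study drugs". There is no discontinuation condition and no time window. The discontinuation part reads: "Discontinuation: maximum of a 30-day gap after the calculated time to finishing the pack based on pack size and number of tablets per day".

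**SAP 2.1** gives the scope of the term study drugs: "Index date is the first prescription date of study drugs, including NOACs, warfarin, and aspirin". Aspirin is therefore one of them.

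Both documents are at version 3.0, dated 03 May 2018, so this is current text on both sides.

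**The concern.** Patients often change anticoagulant directly: the new drug is dispensed while some of the old one is left. Table 3 has no place for that first fill, because its window opens only when the old supply ends. Two things are at stake.

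- **The utilisation endpoint.** Switching, and the clinical events preceding it, are a secondary objective in both documents. A missed direct switch is reported as a discontinuation. A late-dated one can have events that occurred after the change counted as preceding it; Table 3 sets no look-back length that would limit this.
- **The comparative analyses.** The follow-up rule decides which person-time and which events belong to which drug. If Table 3 dates also drive censoring, time after the new fill is charged to the old drug. A programmer working from the protocol and one working from the SAP would build different datasets for the same patient. The scopes differ too: a move from a NOAC to aspirin is a switch in the protocol but cannot be one in Table 3, which bears on sub-datasets 7 to 9.

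**Working it through.** The documents give no figure on this point to reproduce, so the check follows patient timelines through the two definitions.

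**Inputs from the documents:** the 30-day window, discontinuation dated at supply end, and the four reasons for ending follow-up.

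**Assumptions:** pack lengths are not given, so 30, 60 and 90 days are tried. The gap is taken to be in the index drug (Table 3 does not say so). The new OAC is refilled on time. A protocol switch is dated at the first fill of the new drug, and protocol discontinuation at supply end (the protocol does not settle whether the 30 days are added).

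**Set-up.** Index supply ends on day S, so the SAP discontinuation date is D = S. The new OAC is first filled on day s = 1, ..., S + 30 and again every L days. The SAP switch date is the first non-index fill in [D, D + 30], counting day D itself to be generous. With S and L each 30, 60 or 90, there are 3 × (60 + 90 + 120) = 810 timelines.

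**Step 1: can a switch come before discontinuation?** No. The window starts at D, so the switch date is at least D. In none of the 810 timelines was it earlier; at most the two coincided. If Table 3 governs SAP 3.1, the switching criterion is redundant.

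**Step 2: what happens to fills before run-out (s < S)?** The first fill is outside the window. The patient counts as a switcher only if a refill falls inside it.

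| S | L | Early fills | Missed | Counted late | Delay (days) |
|---|---|---|---|---|---|
| 30 | 30 | 29 | 0 | 29 | 30 |
| 30 | 60 | 29 | 29 | 0 | – |
| 30 | 90 | 29 | 29 | 0 | – |
| 60 | 30 | 59 | 0 | 59 | 30 to 60 |
| 60 | 60 | 59 | 29 | 30 | 60 |
| 60 | 90 | 59 | 59 | 0 | – |
| 90 | 30 | 89 | 0 | 89 | 30 to 90 |
| 90 | 60 | 89 | 58 | 31 | 60 |
| 90 | 90 | 89 | 59 | 30 | 90 |

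For S = L = 60, for instance, the refill on day s + 60 is inside [60, 90] only if s ≤ 30. That gives 30 counted late and 59 − 30 = 29 missed.

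**Step 3: one patient.** S = 30, new OAC filled on day 10. Protocol: follow-up ends on day 10. SAP, if Table 3 governs: day 30, so 30 − 10 = 20 days after the new fill stay with the index drug. The switch is dated day 40 if L = 30 and is not recorded if L = 90. By contrast, a first fill on day 40 is a switch on day 40, as intended.

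**Step 4: overlap.** It is S − s days. With s uniform on 1, ..., S − 1 (assumption) the mean is S/2 = 15, 30 or 45 days, with maximum 29, 59 or 89.

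**Step 5: share of person-time.** Assume 10% of patients switch, all before run-out, and mean follow-up is 180 days. The share is 0.10 × (S/2)/180:
- S = 30: 0.10 × 15/180 = 0.83%
- S = 60: 0.10 × 30/180 = 1.67%
- S = 90: 0.10 × 45/180 = 2.5%

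**Step 6: aspirin-index patients.** Suppose such a patient starts an OAC and keeps refilling aspirin. There is no 30-day gap, hence no discontinuation date and no Table 3 switch. Follow-up runs on in the aspirin arm until an outcome or study end, so the overlap is no longer limited by one pack. Under the protocol, a switch to the OAC would end it.

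**The case against.** The best defence is that Table 3 lists utilisation outcomes and is not a censoring rule. SAP 3.1 names switching as an end of follow-up, as the protocol does, and does not point to Table 3. A reader might infer that under the SAP switching never ends follow-up; the SAP does not say this. The inference holds only if Table 3 dating is carried over to SAP 3.1. That part of the defence stands. It leaves SAP 3.1 without any definition of switching, however, and it does nothing for the utilisation endpoint, where Table 3 certainly applies.

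Other points also stand in part:

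- It is tempting to say that every direct switch is lost. The table above shows otherwise: with 30-day refills all are counted, but late. Missed ones remain visible as discontinuations, and Table 3 tabulates preceding events for both patterns.
- A patient who collects the new drug early but finishes the old pack first has no misattributed time, so the overlap days are an upper figure for such patients.
- If the event that prompts a change is itself the outcome under analysis, follow-up for that outcome has already ended. The documents do not show that the overlap clusters around outcome events.
- Aspirin filled alongside a continued OAC is add-on therapy. Exclusion criteria 6 and 7 do not exclude prior antiplatelet users, so a rule that made every aspirin fill a switch would censor concomitant users selectively.

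**Conclusion.** The point holds. Followed as written, Table 3 misses or late-dates OAC-to-OAC switches filled before run-out, which misclassifies a stated secondary endpoint. SAP Table 3, SAP 3.1 and protocol 8.3 also conflict in timing (after discontinuation, or with no such condition) and in scope (OACs only, or any study drug), and must be reconciled. The effect on follow-up is conditional on Table 3 governing censoring. In that case the switching criterion is redundant, overlap days stay with the index drug, and an aspirin-index patient who adds an OAC is not censored for it.

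The size is known only on assumptions: 15 to 45 days per early switcher for 30- to 90-day supplies, or about 0.8% to 2.5% of person-time at 10% switching and 180 days of mean follow-up. The upper end uses the longest supply and should not be quoted alone. These shares exclude the aspirin-index case in step 6, which has no pack-length limit. A reader might go on to say that all nine comparisons are distorted. The documents give no switch rates, pack lengths or event rates, so neither the direction nor the size of any effect on a hazard ratio can be shown.

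**What to change.** 1. **SAP Table 3.** Define a switch as the first fill of a non-index OAC after the index date, dated at that fill, whether it falls before run-out or up to 30 days after. State that the discontinuation gap is in the index drug.
2. **SAP 3.1 and protocol 8.3.** State in the same words that follow-up ends at the earlier of that switch date and discontinuation. Apply this to an OAC fill in aspirin-index patients, whether or not aspirin is continued.
3. **Scope.** Reconcile the protocol's any-study-drug wording with the SAP's OAC-only wording by treating aspirin filled alongside continued OAC fills as concomitant use, not a switch.
4. If the utilisation endpoint is meant to differ from the censoring rule, say so explicitly.

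The cost is a wording change in both documents and a small programming change, with no new data. Because it touches the follow-up definition, it belongs in a protocol amendment as well as the SAP. The downside is slightly shorter follow-up for patients who fill the new OAC early but finish the old pack first.

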**Variables:**

Exposure: The exposure to the following will be considered:

1. Aspirin
2. Aspirin-clopidogrel combination\*
3. Clopidogrel\*
4. Warfarin
5. NOACs
  - Apixaban, Rivaroxaban, Dabigtran

\*[Note] Clopidogrel, Aspirin-clopidogrel will be included in descriptive analysis.

Outcome variables: The following outcomes will be assessed:

1. Effectiveness outcomes
  - Primary outcome: Composite of hemorrhagic stroke, ischemic stroke, and systemic embolism
  - Secondary outcomes: Individual outcome of hemorrhagic stroke, ischemic stroke, and systemic embolism
2. Safety outcomes

- Primary safety outcome: Major bleeding including gastrointestinal bleeding or intracranial bleeding and other bleeding
- Secondary safety outcomes: Individual outcome of major bleeding

**Key-Covariates:** Variables, including, but not limited to, will be age, sex, types of health insurance, CHA2DS2-VASc score, HAS-BLED score, Charlson Comorbidity Index score, etc.

**Data sources:** The Korean Health Insurance Review & Assessment Service (HIRA) database from January 1, 2007 to November 30, 2016 will be used for the analysis. The HIRA database contains the data of universal health insurance system in Korea. The database contains patients' demographic information, their use of inpatient and outpatient services, and pharmacy dispensing claims.

**Study size:** Based on HIRA disease statistics, the number of patients with atrial fibrillation (KCD code: I48) were 148,130 and 169,259 in 2015 and 2016, respectively. Thus, the anticipated number of patients will be approximately 150,000 since we plan to include patients who already had atrial fibrillation and were prescribed with aspirin, warfarin, or NOACs from July 1, 2015 to November 30, 2016. However, the study size might change after applying inclusion and exclusion criteria.

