## 8.6 Data management

### Obtaining data files

Pusan National University team will submit the data request form to HIRA. After the HIRA committee review, the data will be uploaded in the server. The study team will access the data through the remote access using IP address. All medical or pharmacy claims and demographic information from January 1, 2007 to November 30, 2016 of patients with atrial fibrillation (KCD code: I48) from July 1, 2015 to November 30, 2016 will be accessed.

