### **8.9.3 Selection Bias**

This study will include only those patients who filled a prescription through their insurance for aspirin, warfarin, or NOACs. Patients who did not fill a prescription through their insurer (i.e., patients who received free samples or paid for the medication out of pocket) cannot be evaluated in an administrative claims database.

Since the HIRA database does not include eligibility data and the complete mortality data for beneficiaries, the continuous health plan enrollment cannot be ensured and the deceased could be included in the analysis.

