2.2 STUDY OBJECTIVES

Primary objectives

1. To explore baseline characteristics and drug utilization patterns in patients with nonvalvular atrial fibrillation (NVAF) who newly initiated NOACs, warfarin, or used aspirin
 - Demographic and clinical characteristics: Age, sex, types of health insurance, CHA₂DS₂-VASc score, HAS-BLED score, Charlson Comorbidity Index score, etc.
 - Descriptions of index treatment: Types of medication received, index dose intensity
 - Drug utilization pattern: Each patient will be followed-up until the first treatment modification occurs, or study ends (November 30, 2016).
2. To compare effectiveness including hemorrhagic stroke, ischemic stroke and systemic embolism of antithrombotic therapies in patients with NVAF with the following antithrombotic therapies: NOACs, warfarin, and aspirin
 - Primary effectiveness outcome: Composite of hemorrhagic stroke, ischemic stroke, and systemic embolism
 - Secondary effectiveness outcomes: Individual outcome of hemorrhagic stroke, ischemic stroke, and systemic embolism
3. To compare safety of anti-thrombotic therapies in patients with NVAF with the following antithrombotic therapies: NOACs, warfarin, and aspirin
 - Primary safety outcome: Major bleeding including gastrointestinal bleeding or intracranial bleeding and other bleeding
 - Secondary safety outcomes: Individual outcome of major bleeding

[NOTE] comparative analyses will be performed contingent on a feasibility assessment based on the descriptive analyses.

Secondary objectives

1. To explore and understand more detailed drug utilization patterns
 - Standard dose versus reduced dose

- Pattern of usage (i.e., switching, discontinuation) and clinical events preceding the pattern
- Compliance (i.e., medication possession ratio)

2. To compare effectiveness and safety of antithrombotic therapies versus not using therapies among low risk patients (low score of CHA₂DS₂-VASc)

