3 ANALYSIS SETS/ POPULATIONS

3.1 FULL ANALYSIS SET

Inclusion criteria

Patients must meet all of the following inclusion criteria to be eligible for inclusion in the study:

1. Patients aged 18 years or older on the index date
2. Patients had ≥ 1 medical claim for AF (refer to Table 1) before or on the index date with at least one hospitalization or at least two outpatient visits:

[Diagnosis codes for inclusion criteria]

KCD-6 ¹⁾	KCD-7 ²⁾
I48 (Atrial fibrillation and flutter)	I48 (Atrial fibrillation and flutter)
I480 (Atrial fibrillation)	I480 (Paroxysmal atrial fibrillation)
I481 (Atrial flutter)	I481 (Persistent atrial fibrillation)
	I482 (Chronic atrial fibrillation)
	I483 (Typical atrial flutter)
	I484 (Atypical atrial flutter)
	I489 (Atrial fibrillation and atrial flutter, unspecified)

KCD-6, Korean version of ICD-10 (6th revision); KCD-7, Korean version of ICD-10 (7th revision)

1) KCD-6 diagnosis codes will be used from 1 July 2015 to 31 December 2015.

2) KCD-7 diagnosis codes will be used from 1 January 2016 to 30 November 2016.

[NOTE] KCD code is based on ICD-10 and almost similar, but KCD code is slightly different from ICD-10 (e.g., ICD-10 is more subdivided and extensive than KCD code).

3. Patients prescribed aspirin, warfarin, or NOACs in intake period (from July 1, 2015 to November 30, 2016)
[Note] NOACs include apixaban, dabigatran and rivaroxaban.

Exclusion criteria

Patients meeting any of the following criteria will not be included in the study.

1. Medical claims indicating diagnosis or procedure for hip/knee replacement surgery within 6 weeks prior to index date
2. Medical claims indicating a diagnosis code indicative of rheumatic mitral valvular heart disease, mitral valve stenosis during the 12-month baseline period
(Valvular AF / Prosthetic heart valves)
3. Medical claims indicating a diagnosis code of VTE (Venous thromboembolism) during the 12-month baseline period
4. Medical claims indicating a diagnosis or procedure code of transient AF, or cardiac surgery during the 12-month baseline period
(Thyrotoxicosis, Hypertrophic cardiomyopathy, elective defibrillation, radiofrequency ablation, or left atrial appendage occlusion)
5. Medical claims indicating a diagnosis code of others during the 12-month baseline period
 - (End-stage chronic kidney disease / Kidney transplant / Dialysis / Pericarditis)

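### MPR is divided by a fixed 365 days, but patients indexed after 2 December 2015 have less than a year of data, so a late start lowers their score

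*SAP*

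**What the plan says.** Compliance, measured by MPR, is listed under the first secondary objective in both documents (Protocol section 7, SAP section 2.2). The protocol does not define it. The only definition is in SAP section 4.3, Table 3: "Medication possession ratio (MPR) will be calculated as total days of index treatment dispensed / 365 days of study follow-up". The one adjustment is at the top end: "Patients with an MPR greater than 1 will be capped at 1".

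Three other provisions fix how much time a patient can contribute:

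- **Intake.** Under the third inclusion criterion in SAP section 3.1, the qualifying prescription may fall on any day from 1 July 2015 to 30 November 2016.
- **Follow-up.** For drug utilization, SAP section 2.2 says: "Each patient will be followed-up until the first treatment modification occurs, or study ends (November 30, 2016". The follow-up row of Protocol section 8.3 and the end of SAP section 3.1 give the same last date.
- **Data.** Protocol section 8.6 describes the extract as "All medical or pharmacy claims and demographic information from January 1, 2007 to November 30, 2016". The data-source paragraph of the protocol abstract agrees.

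**The concern.** Intake, follow-up and data all close on the same day, so the last patients to enter have almost no observable time. Dividing every patient's dispensed days by 365 treats the unobserved remainder of the year as days without drug. For later starters the score then depends partly on when they entered, whatever their compliance.

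This is not a constant scaling that cancels between drugs. Two drugs with identical compliance would show different MPRs if one was taken up earlier in the 17-month intake than the other. Such a difference is plausible here: aspirin users may have had prior antithrombotic treatment, while NOAC users must be free of oral anticoagulants for a year. The documents give no index-date distribution for any drug, so neither the size nor the direction of a between-drug distortion can be derived from them.

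**Working it through.** **Inputs from the documents.** Intake is 1 July 2015 to 30 November 2016 (SAP 3.1). The end of follow-up and data is 30 November 2016 (SAP 2.2 and 3.1; Protocol 8.3 and 8.6). The denominator is 365 and the cap is 1 (SAP 4.3). The plan gives no MPR figure to reproduce.

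**Assumptions.** The index day is counted. Start patterns over intake and pack sizes of 30 to 90 days are mine; the documents give neither.

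**1. Days available.** Let d = days from index date to 30 November 2016, inclusive.

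- Number of index dates: 184 (July to December 2015) + 335 (January to November 2016) = 519, so d runs from 519 down to 1.
- Index on 2 December 2015: 30 + 335 = 365 days. Index on 3 December 2015: 364 days.
- Dates with d ≥ 365: 153 (July to November) + 2 = 155, or 155/519 = 29.9%.
- Dates with d < 365: 364, or 364/519 = 70.1%.

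If the index day is not counted, the cut-off moves by one day.

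**2. Score of a fully covered patient, supply counted to the end of data.** MPR = min(1, d/365).

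| Index date | d | MPR |
|---|---|---|
| 2 Dec 2015 | 365 | 1.00 |
| 1 Mar 2016 | 275 | 0.75 |
| 1 Jun 2016 | 183 | 0.50 |
| 1 Sep 2016 | 91 | 0.25 |
| 30 Nov 2016 | 1 | 0.003 |

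**3. Averages under assumed start patterns.** With uniform starts the mean is (155 + Σd/365 for d = 1 to 364)/519 = (155 + 66,430/365)/519 = (155 + 182)/519 = 0.649. For the other two patterns each date is weighted by d (linearly falling starts) or by 520 − d (linearly rising starts).

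| Starts over intake | Share of patients with d < 365 | Mean MPR, all fully covered |
|---|---|---|
| Linearly falling | 0.492 | 0.835 |
| Uniform | 0.701 | 0.649 |
| Linearly rising | 0.910 | 0.463 |

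**4. Last fill counted whole.** Table 3 does not say whether supply running past the end of data enters the numerator. If it does, MPR = min(1, ⌈d/p⌉ × p/365) for pack size p. Over every whole p from 30 to 90:

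- dates that still cannot reach 1.00: from 292/519 = 56.3% (p = 73) to 364/519 = 70.1% (p = 52);
- mean with uniform starts: from 0.677 (p = 30) to 0.734 (p = 90);
- index on 1 September 2016: from 92/365 = 0.25 (p = 46) to 180/365 = 0.49 (p = 90).

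**5. Using each patient's own observable time.** This is the obvious alternative, and without a minimum it has its own artefact. One 30-day fill and nothing more scores 30/519 = 0.06 for an index on 1 July 2015, but 1.00 for any index on 1 to 30 November 2016. With a 180-day minimum, as an example, the range narrows to 0.06 to 30/180 = 0.17 and 340 of 519 dates (65.5%) are kept. With a common 365-day window the same patient scores 30/365 = 0.08 at every eligible date.

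**The case against.** The strongest reply is that the denominator in Table 3 refers to a year of study follow-up, not to a bare 365, and so may be meant to cover only patients who have that year. On that reading nothing is biased and the gap is an unwritten eligibility rule. The reading is possible, but neither document writes the restriction, and the SAP admits and follows patients up to 30 November 2016. Two programmers could build different cohorts from the same line, so the text needs changing on either reading.

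Second, the numerator is days dispensed, so a pack running past the end of data softens the ceiling. That is right: with 30-, 60- or 90-day packs, 4 of the 364 late dates can still reach 1.00, and with 73-day packs 72 can. The dependence on index date remains.

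Third, the consequence is limited. MPR is exploratory, has no table shell and no row of its own in the summary of analyses, and is not a covariate in SAP section 4.4. No passage names a between-drug comparison of MPR, although SAP sections 5.1 and 6 provide tests for outcome variables and utilization patterns. This point stands and sets the weight of the finding.

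Fourth, limiting MPR to early starters changes the population described. That also stands; it is a cost of the fix.

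**Conclusion.** The concern holds. As written, MPR does not measure compliance for patients indexed after 2 December 2015. The firm figure is calendar arithmetic: 364 of 519 index dates (70.1%) leave less than the 365 days in the denominator. The share of patients affected (49% to 91%) and the mean score of fully covered patients (0.46 to 0.84) rest on assumed start patterns and illustrate scale; they are not estimates of the bias. Counting the last fill whole reduces the effect but does not remove it at any pack size from 30 to 90 days.

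This should be corrected before the compliance analysis is run, because MPR is a named secondary objective. It does not affect the effectiveness or safety hazard ratios.

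**What to change.** In SAP Table 3:

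1. Restrict MPR to patients indexed by 2 December 2015, take numerator and denominator from the same first 365 days, count only supply falling inside that window, and keep the cap at 1.
2. State how patients who discontinue or switch within the year are handled, since utilization follow-up ends at the first treatment modification. Either their remaining days count as not possessed, or they are reported separately.
3. If the remaining days count, note that time after an unrecorded death would also count as non-possession. Protocol section 8.9.3 concedes that "the continuous health plan enrollment cannot be ensured and the deceased could be included in the analysis".

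If the sponsor prefers to keep later starters, it could use each patient's own observable time, set a minimum observation period, and report MPR by length of observation. A minimum narrows the dependence on index date but does not remove it.

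The cost is one SAP definition and minor programming. Under the first option, patients from the later 70% of index dates leave this one descriptive analysis, so the result describes starters from July to early December 2015 only and should be labelled so. No other analysis changes.
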